The primary efficacy endpoint is ORR for subjects with measurable disease and BOR for all subjects. All ORR or BOR will be based on RECIST 1.1 assessed every 8 weeks.

The analyses will be descriptively performed on the Safety Analysis Set.

Cohort 2B: Osteosarcoma

The primary efficacy endpoint is PFS-4 based on RECIST 1.1.

The null hypothesis that PFS-4 is $\leq 25\%$ will be tested against the alternative hypothesis of a PFS-4 $\geq 45\%$, using the 1-sample exact test of a single proportion, at the 1-sided 0.1 level. PFS-4 will be presented with corresponding 2-sided, exact binomial 80% and 95% CIs. This analysis will be performed on the Safety Analysis Set.

Cohort 3: Combination Dose-Finding and Expansion)

Cohort 3A: Osteosarcoma Combination Dose-Finding

As in Cohort 1, the DLT will be assessed to determine the RD of lenvatinib in combination with chemotherapy (ifosfamide and etoposide). DLTs occurring during Cycle 1 will be evaluated and the subjects will be assigned a dose based on the rules for Dose-Escalation and De-Escalation (refer to Section [Study Design Treatment Phase: Cohort 3A](#)).

Cohort 3B: Osteosarcoma Combination Expansion

The primary efficacy endpoint is PFS-4 based on RECIST 1.1.

The null hypothesis that PFS-4 is $\leq 25\%$ will be tested against the alternative hypothesis of a PFS-4 $\geq 50\%$, using the 1-sample exact test of a single proportion, at the 1-sided 0.1 level. PFS-4 will be presented with corresponding 2-sided, exact binomial 80% and 95% CIs. This analysis will be performed on the lenvatinib-naïve subjects in Safety Analysis Set, while subjects enrolled from Cohorts 1 and 2B will only be summarized as appropriate.

Secondary Endpoint Analyses

The secondary endpoints of PFS and TTP will be analyzed using Kaplan-Meier product-limit estimates. Median PFS, and the cumulative probability of PFS at 4 and 12 months will be presented with 2-sided, 95% CIs when an adequate number of at risk subjects at those time

points warrant the estimate. The cumulative PFS and TTP probabilities will be plotted over time as appropriate.

The secondary endpoints of ORR, DCR, and CBR will be calculated with exact binomial 95% CIs.

The endpoint of OS will be analyzed using Kaplan-Meier product-limit estimates. Median OS and the cumulative probability of OS at 12 months will be presented with 2-sided, 95% CIs when an adequate number of at risk subjects at those time points warrant the estimate.

The above analyses will be based on the lenvatinib-naïve subjects in Safety Analysis Set, while other subjects enrolled from Cohorts 1 and 2B will be summarized for these endpoints as appropriate.

Pharmacokinetic, Pharmacodynamic, and Pharmacogenomic/Pharmacogenetic Analyses

Plasma concentrations of lenvatinib versus time data will be listed. Plasma concentrations of lenvatinib versus time data will be analyzed using a population PK approach to estimate population PK parameters. The analysis will be detailed in an analysis plan at a later date.

Correlation between clinical response to lenvatinib treatment and blood or tumor biomarkers may be examined using descriptive statistics and graphic displays as appropriate. If conducted, a detailed analysis plan will be provided in a separate document.

Exploratory/graphical analyses will be conducted for PK/PD evaluations, and may be followed by model based analyses. If conducted, a detailed analysis plan will be provided in a separate document at a later date.

Safety Analyses

The incidence of treatment-emergent adverse events (TEAEs) and SAEs will be summarized by study cohort, dose-level, and group. Laboratory test data, vital signs, 12-lead ECGs, urine dipstick, occult blood in stool, Lansky play scores or Karnofsky performance scores, physical examination, height, and proximal tibial growth plates at scheduled time points and their changes from baseline will be summarized by study cohort and group using descriptive statistics, as appropriate. Abnormal values will be flagged. Prior and concomitant medications, medical/surgical history, and subject demographics will be summarized and listed by study cohort and group.

Other Analyses

Measurement of palatability will be assessed using the Hedonic scale (Guinard, 2001) which is a Visual Analog Scale (VAS).

Interim Analyses

Interim analyses may be performed after consultation with the PSC.

The sponsor will closely evaluate the risks and benefits of the study throughout its conduct, along with the PSC as needed.

Sample Size Rationale

Approximately 69 to 108 subjects are planned for this study.

Cohort 1 (Single-Agent Dose-Finding)

Approximately 12 to 24 subjects based on TiTE-CRM algorithm ([Cheung and Chappell, 2000](#)).

Cohort 2 (Single-Agent Expansion)

Approximately 27 to 42 subjects: DTC group (12 subjects) and osteosarcoma group (15 to 30 subjects).

Cohort 2A: DTC Group

Approximately 12 subjects with evaluable or measurable disease are planned to be enrolled in Cohort 2A due to limited number of pediatric patients with DTC.

Cohort 2B: Osteosarcoma Group

A minimum of 15 PFS-4 evaluable subjects will be assessed in cohort 2B. The sample size estimates were based on Simon's Optimal Two-Stage Design ([Simon, 1989](#)). If fewer than 5 subjects who are alive and free of disease progression at 4 months after first dose date are observed among the 15 evaluable subjects in Stage I, accrual in the cohort will be suspended. Otherwise, if at any time during Stage I of the cohort, at least 5 subjects who are alive and free of disease progression at 4 months after first dose date are recorded among the 15 evaluable subjects, enrollment in the cohort will continue seamlessly for a total of approximately 27 evaluable subjects. If, at the end of the second stage for the cohort, at least 10 subjects who are alive and free of disease progression at 4 months are recorded among the 27 subjects in the cohort, study drug will be considered active in the population.

The above sample size estimates are based on the following assumptions: the null hypothesis PFS-4 (H_0) is $\leq 25\%$, and the alternative hypothesis PFS-4 (H_1) is $\geq 45\%$. One-sided Type I error (α) = 0.1, and power = 80%. To account for nonevaluable subjects, a total of 15-30 osteosarcoma subjects will be enrolled for Cohort 2B.

Cohort 3 (Combination Dose-Finding and Expansion)

Cohort 3A (Combination Dose-Finding)

Approximately 12 to 24 osteosarcoma subjects for whom ifosfamide and etoposide are

considered a treatment option

Cohort 3B (Combination Expansion)

With the following assumptions: $p_0=25\%$, $p_1=50\%$, 1-sided $\alpha=10\%$, $\beta=20\%$, where p_0 is an unacceptable rate of PFS, p_1 is the target rate of PFS, α is the probability of declaring lenvatinib effective when the true rate is p_0 , and β is the probability of declaring lenvatinib not effective if the true rate is p_1 , a sample size of 15 subjects will provide a statistical power of 80%. To account for nonevaluable subjects, a total of 18 lenvatinib-naïve subjects will be enrolled for Cohort 3B, along with some subjects enrolled from Cohorts 1 and 2B.

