15. Osteosarcoma subjects receiving combination therapy of lenvatinib with ifosfamide and etoposide should meet all the exclusion criteria, with the exception of Criterion Number 6

Study Treatment

Additional details are provided in the Study Design section under [Treatment Phase](#).

Test drug: Lenvatinib

Lenvatinib will be provided as hard capsules containing 1, 4, or 10 mg lenvatinib. Lenvatinib will be administered orally QD. The maximum dose administered during the study should not exceed 24 mg QD in any of the cohorts. An extemporaneous suspension of lenvatinib capsules should be used for children unable to swallow capsules, as detailed in [Appendix 12](#).

Cohort 1 (Single-Agent Dose-Finding)

Subjects 6 to <18 years: Lenvatinib will be administered orally QD. Study drug doses for Cohort 1 are displayed in the table below. The starting dose is 11 mg/m² QD, which is 80% of the adult RD of 24 mg QD. The 80% starting dose is based on consensus reached for pediatric Phase 1 trials ([Smith, et al., 1998](#); [Lee, et al., 2005](#)). If the dose of 11 mg/m² (Dose Level 1) is not safe and tolerable, subjects will receive lenvatinib at the lower de-escalation dose of 9 mg/m² (Dose Level -1).

Lenvatinib Doses for Single-Agent Dose-Finding (Cohort 1)

Dose Level	Lenvatinib Once-Daily
-1	9 mg/m ²
1 (starting dose)	11 mg/m ²
2	14 mg/m ²
3	17 mg/m ²

Body surface area (BSA) must be calculated on Day 1 of each cycle based on the subject's current height and body weight. BSA will be used to determine the amount of lenvatinib for

each subject. The dose should be rounded to the nearest whole number.

Subjects 2 to <6 years: Subjects will receive 5 mg/m² during the 21-day Run-In Period. If these subjects do not experience any DLT, they will enter Cohort 1 Cycle 1 Day 1 and intrasubject dose escalation will take place as detailed in the Study Design section ([Treatment Phase: Cohort 1](#)).

Cohorts 2A and 2B (Single-Agent Expansion)

Lenvatinib will be administered orally QD at the RD. The RD of Single-Agent lenvatinib determined in Cohort 1 is 14 mg/m² as recommended by TiTE-CRM and confirmed by PSC. Subjects in Cohorts 2A and 2B will receive 14 mg/m² lenvatinib (equivalent to 24 mg QD, adult daily dose). After adjustment for BSA, the daily dose should not exceed 24 mg QD.

Cohort 3A (Combination Dose Finding)

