Lenvatinib will be administered in combination with ifosfamide and etoposide to osteosarcoma subjects as described in the Study Design section ([Treatment Phase: Cohort 3A](#)). Lower doses may be administered depending on the safety information.

Cohort 3B (Combination Expansion)

Subjects will receive lenvatinib at the RD determined to be safe and tolerable in Cohort 3A (Combination Dose-Finding) in combination with ifosfamide and etoposide.

The chemotherapy cycles in Cohorts 3A and 3B will be repeated every 21 days.

Lenvatinib Dose Reduction and Interruption Instructions

Dose adjustments will be made for subjects who experience treatment-related toxicity according to the guidelines provided in the table below. Doses in the Dose Adjustment column are based on a presumed starting dose of 11 mg/m².

Dose reductions will occur in succession based on the previous dose level. Each dose level reduction is a 20% reduction from the previous dose. Once the dose has been reduced, it cannot be increased at a later date.

Criteria for Temporary Discontinuation of Study Drug, Dose Reduction, and Resumption of Treatment

Treatment-Related Toxicity ^{a,b} including hepatic injury and thromboembolic events	Management	Dose Adjustment
Grade 1		
	Continue treatment	No change
Intolerable Grade 2^c or Grade 3^c		

First occurrence	Interrupt until resolved to Grade 0-1 or baseline	8.8 mg/m ² (or 20% reduction of the starting dose) orally once daily (QD) (one-level reduction)
Second occurrence (same toxicity or new toxicity)	Interrupt until resolved to Grade 0-1 or baseline	7.0 mg/m ² (or 20% reduction of the previous dose) orally QD (one-level reduction)
Third occurrence (same toxicity or new toxicity)	Interrupt until resolved to Grade 0-1 or baseline	5.6 mg/m ² (or 20% reduction of the previous dose) orally QD (one-level reduction)
Fourth occurrence (same toxicity or new toxicity)	Interrupt until resolved to Grade 0-1 or baseline	Discuss with sponsor

Grade 4^a: Discontinue Study Treatment

Note: For grading see Common Terminology Criteria for Adverse Events version 4.0 ([Appendix 2](#)). Collect all CTC grades of adverse events, decreasing and increasing grade.

- a: Interruption of lenvatinib treatment for more than 28 days (due to lenvatinib-related toxicities) will require a discussion with the sponsor before treatment can be resumed.

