During the Treatment Period, subjects with systolic BP \geq 99th percentile [BP \geq 160 mm Hg] or diastolic BP \geq 99th percentile [BP \geq 100 mm Hg] must have their BP monitored every 2 weeks (on Day 15 or more frequently as clinically indicated) until systolic BP has been <95th percentile [\leq 150 mm Hg] and diastolic BP has been <95th percentile [\leq 95 mm Hg] for 3 consecutive months. If a new event of systolic BP \geq 99th percentile [BP \geq 160 mm Hg] or diastolic BP \geq 99th percentile [BP \geq 100 mm Hg] occurs, the subject must resume the Day 15 evaluation until systolic BP has been <95th percentile [\leq 150 mm Hg] and diastolic BP has been <95th percentile [\leq 95 mm Hg] for 3 consecutive months.

The following guidelines should be followed for the management of systolic BP \geq 99th percentile [BP \geq 160 mm Hg] or diastolic BP \geq 99th percentile [BP \geq 100 mm Hg] confirmed on repeat measurements after an hour:

- Continue lenvatinib and institute antihypertensive therapy for subjects not already receiving antihypertensive medication.

- For those subjects already on antihypertensive medication, the dose of the current agent may be increased, if appropriate, or 1 or more agents of a different class of antihypertensive should be added.
- If systolic BP \geq 99th percentile [BP \geq 160 mm Hg] or diastolic BP \geq 99th percentile [BP \geq 100 mm Hg] persists despite maximal antihypertensive therapy, then lenvatinib administration should be interrupted and restarted at a lower dose QD (one dose level reduction [20%] as specified in the table above) only when systolic BP $<$ 95th percentile [\leq 150 mm Hg] and diastolic BP $<$ 95th percentile [BP \leq 95 mm Hg] and the subject has been on a stable dose of antihypertensive medication for at least 48 hours.
 - If systolic BP \geq 99th percentile [BP \geq 160 mm Hg] or diastolic BP \geq 99th percentile [BP \geq 100 mm Hg] recurs despite optimal management of hypertension with antihypertensive medications (either by dose increase or the addition of a different class of antihypertensive), then lenvatinib administration should be interrupted and restarted at a lower dose QD (one dose level reduction [20%] as specified in the table above) only when systolic BP $<$ 95th percentile [BP \leq 150 mm Hg] and diastolic BP $<$ 95th percentile [BP \leq 95 mm Hg] and the subject has been on a stable dose of antihypertensive medication for at least 48 hours.

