9.1.2.2 Cohort 2 (Single-Agent Expansion)

Cohort 2 will begin enrollment after the RD of lenvatinib is identified in Cohort 1. The efficacy of lenvatinib will be evaluated in 2 malignancy groups separately: DTC (Cohort 2A) and osteosarcoma (Cohort 2B). Subjects will be treated at the RD identified in Cohort 1. The RD of Single-Agent lenvatinib determined in Cohort 1 is 14 mg/m² as recommended by TiTE-CRM and confirmed by PSC. Subjects in Cohorts 2A and 2B will receive 14 mg/m² lenvatinib (equivalent to 24 mg QD, adult daily dose). After adjustment for BSA, the daily dose should not exceed 24 mg QD.

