9.4 Treatment

9.4.1 Treatment(s) Administered

Lenvatinib will be provided by Eisai as hard capsules containing 1, 4, or 10 mg lenvatinib. An extemporaneous suspension of lenvatinib capsules should be used for children unable to swallow capsules, as detailed in [Appendix 12](#).

Cohort 1 (Single-Agent Dose-Finding): Lenvatinib will be administered orally QD on Days 1 to 28 of each 28-day cycle ([Table 1](#)).

Cohort 2 (Single-Agent Expansion): Lenvatinib will be administered orally QD at the Single-Agent RD (identified in Cohort 1) on Days 1 to 28 of each 28-day cycle.

Cohort 3A (Combination Dose-Finding): Lenvatinib will be administered orally QD on Days 1 to 21 of each 21-day cycle ([Table 2](#))

Cohort 3B (Combination Expansion): Lenvatinib will be administered orally QD at the RD (identified in Cohort 3A) on Days 1 to 21 of each 21-day cycle. Ifosfamide and etoposide will be administered on Days 1 to 3 of each 21-day cycle.

Before dose administration on Day 1 of each cycle and prior to a change in dose due to dose reduction, the amount of lenvatinib needed for each subject must be calculated as follows:

$$\text{Scheduled dose (mg/m}^2\text{)} \times \text{body surface area (BSA) (m}^2\text{)} = \text{lenvatinib dose (mg)}$$

BSA will be calculated using the method that is accepted and customarily used by the clinical site. BSA must be calculated on Day 1 of each cycle based on the subject's current height and body weight. BSA will be used to determine the amount of lenvatinib for each subject. BSA should not be corrected for amputation. The dose should be rounded to the nearest whole number. After adjustment for BSA, the daily dose of lenvatinib should not exceed 24 mg daily.

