- e. Obese subjects with weight loss do not need to return to baseline or Grade 1 weight loss to restart lenvatinib. There should be no weight loss for at least 1 week, and subjects should be started at the lower dose and normal BMI should be used for future dose reductions. Obesity is defined as body mass index (BMI) percentiles corresponding to 30 kg/m², related to the age of the children. ([Cole T.J., et al 2000](#)) or BMI \geq the 95th percentile for children and teens of the same age and sex ([Ogden CL et al, 2002](#)) ([Appendix 9](#) and [10](#)).

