3.4.2 Doses for Cohorts 3A and 3B

The RD of the combination with ifosfamide and etoposide determined in Cohort 3A is lenvatinib 14 mg/m²/day + ifosfamide 3000 mg/m²/day and etoposide 100 mg/m²/day as recommended by the above rules and confirmed by the PSC.

Cohort 3B will receive lenvatinib 14 mg/m²/day + ifosfamide 3000 mg/m²/day and etoposide 100 mg/m²/day.

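### For subjects capped at 24 mg, the text leaves the first lenvatinib reduction open to two readings, and the mg/m² reading gives no reduction at all from a BSA of about 2.10 m²

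*Protocol*

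**What the plan says.** Protocol 9.1.2.2 gives the single-agent dose for Cohorts 2A and 2B as 14 mg/m², "as recommended by TiTE-CRM and confirmed by PSC". SAP 3.4.2 adds: "Cohort 3B will receive lenvatinib 14 mg/m²/day". On the cap, the synopsis states: "After adjustment for BSA, the daily dose should not exceed 24 mg QD"; Section 9.4.1 repeats this limit.

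On reductions, the synopsis and Section 9.4.1.2 both state: "Each dose level reduction is a 20% reduction from the previous dose". They also tie successive reductions to the previous dose level, and Table 3 lists the levels in mg/m² from a presumed start of 11 mg/m².

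Section 9.4.1 then sets the calculation: "prior to a change in dose due to dose reduction, the amount of lenvatinib needed for each subject must be calculated", as scheduled mg/m² times BSA. The result is rounded to a whole mg, and the cap applies after the BSA adjustment.

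For blood pressure that stays at or above the 99th percentile, or returns there, the synopsis has lenvatinib interrupted and then "restarted at a lower dose QD (one dose level reduction [20%] as specified in the table above"; Section 9.4.1.4 has a parallel instruction.

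The only reduction rule that refers to body size is footnote e of Table 3: "subjects should be started at the lower dose and normal BMI should be used for future dose reductions". It covers obese subjects with weight loss and does not mention the cap.

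**The concern.** A capped subject takes fewer mg/m² than assigned. If the 20% step is applied to the assigned 14 mg/m², it lowers a level the subject was not receiving, and the cap absorbs part or all of the step. The fall in the mg dose actually taken shrinks as BSA rises and eventually disappears.

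The reduction is the planned response to Grade 3 or intolerable Grade 2 toxicity and to severe hypertension that persists on treatment. At stake is whether a large subject who has stopped for such toxicity could be restarted on the dose that produced it, at the first of three preset steps. Two sites could also give different doses to the same patient.

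**Working it through.** **Inputs.** Assigned level 14 mg/m² (Protocol 9.1.2.2; SAP 3.4.2). Step factor 0.8 (Protocol 9.4.1.2). Formula, whole-mg rounding and 24 mg cap (Protocol 9.4.1).

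**The plan's own figures.** From 11 mg/m²: 11 × 0.8 = 8.8; 8.8 × 0.8 = 7.04; 7.04 × 0.8 = 5.63. These match Table 3 (8.8, 7.0, 5.6), so the table applies successive 20% steps on the mg/m² scale.

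**The same scale from 14 mg/m².** 14 × 0.8 = 11.2; then 8.96; then 7.168 mg/m².

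**Dose.** mg dose = min(24, round(level × BSA)).

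- At 14 mg/m², the cap changes the rounded dose from 24.5/14 = 1.750 m².
- At 11.2 mg/m², the rounded dose reaches m mg at BSA = (m − 0.5)/11.2.

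| BSA (m²) | Before | After first reduction | Cut in mg taken |
|---|---|---|---|
| 1.750 to <1.830 | 24 | 20 | 4/24 = 16.7% |
| 1.830 to <1.920 | 24 | 21 | 3/24 = 12.5% |
| 1.920 (21.5/11.2) to <2.009 | 24 | 22 | 2/24 = 8.3% |
| 2.009 (22.5/11.2) to <2.098 | 24 | 23 | 1/24 = 4.2% |
| 2.098 (23.5/11.2) or more | 24 | 24 | 0% |

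The cap, not rounding, causes the nil cut: without rounding it would still occur, from 24/11.2 = 2.143 m².

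**Worked case, BSA 2.10 m².**

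- Assigned: 14 × 2.10 = 29.4, capped to 24 mg.
- First reduction: 11.2 × 2.10 = 23.5, rounded to 24 mg.
- Second: 8.96 × 2.10 = 18.8, rounded to 19 mg.
- Third: 7.168 × 2.10 = 15.05, rounded to 15 mg.

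**The other reading, 20% off the mg dose taken.** 24 × 0.8 = 19.2, rounded to 19 mg; 24 × 0.64 = 15.4, rounded to 15 mg; 24 × 0.512 = 12.3, rounded to 12 mg. This holds at every BSA where the cap applies.

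**How large these subjects are.** 24/14 = 1.714 m² is the BSA at which 14 mg/m² equals 24 mg. The nil-cut threshold is 2.098/1.714 = 1.22 times that. Osteosarcoma subjects may be up to 25 years old, so adult-sized subjects are eligible. The documents give no BSA distribution.

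**The case against.** The strongest reply is that nothing forces a 24-to-24 mg restart. Section 9.4.1 does not say that the scheduled level after a reduction is 80% of the assigned level. The previous dose of a capped subject is 24 mg. At 2.10 m² that is 24/2.10 = 11.43 mg/m²; 80% of it is 9.14 mg/m²; times 2.10 is 19.2, so 19 mg. That satisfies the 20% rule, the formula, the rounding, the cap and the instruction to restart lower. Section 9.1.2.3 also recognises that capped subjects take less than their assigned level. This objection stands in part. A reader might infer that the protocol prescribes a zero reduction, and the documents do not support that. But 9.1.2.3 uses the distinction only for counting dose-limiting toxicities in Cohort 3A, while Table 3 and the reference to dose levels point to the mg/m² scale. Both readings are open and no sentence chooses between them.

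A second reply is that the capped subject is already below the assigned level: 11.43 mg/m² is about 18% under 14. Measured against the uncapped 29.4 mg, the third-step dose of 15 mg is a 49% cut, in line with three 20% steps (1 − 0.8³ = 48.8%). This is correct, but the toxicity arose at the 24 mg taken, and the hypertension text requires a lower dose.

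A reader might also treat 1.92 m² as the point where the rule fails. No document sets such a line. Rounding alone can shrink an uncapped subject's step to 11.1% (9 to 8 mg near 0.67 m²), and between 1.920 and 2.098 m² the restarted dose is still lower. Only from 2.098 m² is it unchanged.

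**Conclusion.** The point holds as an unresolved ambiguity with a specific failing case, and it is minor. On the mg/m² reading, a subject at 14 mg/m² with a BSA of 2.098 m² or more gets no reduction at the first step, contrary to two other instructions. The printed levels in Table 3 are correct.

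The size rests on whole-mg rounding, the 24 mg cap and a site applying the step to the assigned level. How many subjects this would reach is unknown: it needs a large BSA, a qualifying toxicity and that reading. Other safeguards remain: interruption until recovery, later steps that do lower the dose, discontinuation at Grade 4 and sponsor discussion at a fourth occurrence.

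A reader might infer an effect on the efficacy results or the dose-level summaries. The documents do not support that: no endpoint definition depends on the size of a reduction, and SAP 5.3.6 keeps the expansion cohorts at their planned level whether or not the dose is capped.

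**What to change.** In Protocol 9.4.1, 9.4.1.2 and the synopsis, add: *After a dose reduction the restarted mg dose must be lower than the mg dose last taken, including for subjects capped at 24 mg.*

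This costs one sentence in three places, with no added patients, visits or procedures. At the first reduction from 14 mg/m² it changes the mg/m² calculation only for subjects of 2.098 m² or more.

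The sentence does not set the size of the cut. Whether capped subjects should have the full 20% taken from the mg dose received (24, 19, 15, 12 mg) is a dosing choice for the sponsor. It would give every capped subject a real 20% step, at the price of lower exposure after a reduction: at 2.10 m², 19 mg is 9.0 mg/m². If the sponsor chooses it, the text should say so and carry the corresponding lower mg/m² level into later Day 1 calculations.
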